13.0 Treatment/Follow-up Decision at Evaluation of Patient

Follow-up data will be collected and entered in accordance to Section 4.0. No follow-up data is required beyond 5 years from the date of study enrolment.

13.1 If a patient fails to complete the entire course of treatment for reasons other than toxicity or prostate cancer progression, he will be regarded as *inevaluable* and will be replaced. Baseline characteristics will be collected in the database. However, no further data collection will be collected.

13.2 A patient is deemed *ineligible* if after registration, it is determined that at the time of registration, he did not satisfy each and every eligibility criteria for study entry.

The patient may continue treatment off-protocol at the discretion of the physician as long as there are no safety concerns, and the patient was properly registered.

If the patient received treatment, all data up until the point of confirmation of ineligibility must be submitted, and collection of follow-up data will continue in accordance to Section 4.0. Event monitoring will be required per Section 18.0 of the protocol.

- 13.3 A patient is deemed a *cancel* if he is removed from the study for any reason before any study treatment is given. On-study material and the End of Active Treatment/Cancel Notification Form must be submitted. No further data submission is necessary.
- 13.4 A patient is deemed a *major violation*, if protocol requirements regarding treatment are severely violated such that evaluability for primary end point is questionable. All data up until the point of confirmation of a major violation must be submitted. The patient will continue the active monitoring phase and the event-monitoring phase of the study. The patient may continue treatment off-protocol at the discretion of the physician as long as there are no safety concerns, and the patient was properly registered.
- 13.5 When the patient develops a biochemical recurrence only, he will continue on the protocol test schedule until further medical management is implemented at the discretion of his physician.
- 13.6 When the patient develops a local, regional, or distant recurrence, he will go off study with no further scheduled follow-up tests.

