18.0 Records and Data Collection Procedures

18.1 Submission Timetable

Initial Material(s)

CRF	Baseline (Compliance with Test Schedule Section 4.0)
Demographics	
Patient Eligibility	
On-Study	≤2 weeks after registration
Adverse Events-Baseline	
PSA and Testosterone Values	
Prostate Radiotherapy Questionnaires	*6 months from accrual
Androgen Deprivation Treatment	

Test Schedule Material(s)

CRF	Active-Monitoring Phase ² (Compliance with Test Schedule Section 4.0)	Event-Monitoring Phase ³ (Compliance with Test Schedule Section 4.0)

	On-Study	At each evaluation during treatment	At end of treatment	Post-RT: 3, 6, 12, 18, and 24 months (Active Monitoring)	Post-RT: 30, 36, 42, 48, and 60 months (Event Monitor)
Adverse Event: Solicited Form	X	X	X	X	X
Adverse Events Other	X	X ¹	X ¹	X ¹	X ¹
Radiation Treatment			X		
Androgen Deprivation Treatment	X	X ⁴	X ⁴	X ⁴	X ⁴
End of Active Treatment			X		
PSA and Testosterone Values		X		X ⁵	X ⁵
Adverse Events: Post Radiation Treatment				X	X
Post Radiation Patient Status/Assessment				X	X ⁶
Prostate Radiotherapy Questionnaires				X	X
Consent Withdrawal form		X ¹	X ¹	X ¹	X ¹
Lost to Follow-up		X ¹	X ¹	X ¹	X ¹

1. When applicable
2. Post RT (Active monitoring phase): 3 months (+/- 1 months), 6 months (+/- 1 months), 12 months (+/- 1 months), 18 months (+/- 1 months), and 24 months (+/- 1 months) post RT.
3. Post RT (Event-monitoring phase): 30 months (+/- 1 months), 36 months (+/- 1 months), 42 months (+/- 1 months), 48 months (+/- 1 months), 54 months (+/- 1 months), and 60 months (+/- 1 months) post RT.
4. Coordinator will look to see if patient received Androgen Deprivation Therapy since the previous reporting period. If there was no change, indicate on form.
5. Testosterone is collected at post-RT month 12, 24, 36, 48, and 60 months post RT. However, if one was completed it should be entered into the CRF. Therefore, the form will populate at each visit, and if it wasn't completed because it was not required, indicate "not completed" on form.
6. History, physical exam, and ECOG are not required during Event Monitoring Phase.

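### Patients leave the study at clinical recurrence with no required survival follow-up, which would bias 5-year disease-specific and overall survival upward

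*Combined protocol and SAP*

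**What the plan says.** Sections 2.2.4 and 2.2.5 list disease-specific and overall survival at 5 years as secondary goals. Sections 16.3.2.2 and 16.3.2.3 estimate both by Kaplan-Meier at 2 and 5 years and say nothing about when a patient who has left the study is censored. Section 11.2.6 counts two kinds of death for disease-specific survival: those the investigator attributes to prostate cancer, and those from complications of treatment.

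Section 13.6 sets the rule at clinical recurrence: "When the patient develops a local, regional, or distant recurrence, he will go off study with no further scheduled follow-up tests". Other parts of Section 13 are more explicit, in both directions:

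- **Data stop.** For inevaluable patients (13.1): "However, no further data collection will be collected". For cancels (13.3): "No further data submission is necessary".
- **Data continue.** For treated ineligible patients (13.2): "Event monitoring will be required per Section 18.0 of the protocol". For major violations (13.4): "The patient will continue the active monitoring phase and the event-monitoring phase of the study".
- **PSA relapse only (13.5).** "he will continue on the protocol test schedule until further medical management is implemented at the discretion of his physician". What follows is not stated.
- **Overall limit (13.0).** "No follow-up data is required beyond 5 years from the date of study enrolment".

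**The concern.** Clinical recurrence normally precedes death from prostate cancer. A rule that ends follow-up at recurrence therefore removes the patients who would supply most disease-specific events, at the moment their risk goes up. Kaplan-Meier assumes that censored patients carry the same later risk as those still followed, and here they would not.

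Disease-specific survival would be close to 100% by construction, apart from treatment-complication deaths that are still counted. Overall survival would approach the survival of recurrence-free men. Neither figure would say much about disease control, yet both will be reported, and Section 1.8 foresees this study as a basis for a phase III trial.

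There is a smaller side effect. A patient who recurs clinically before post-RT month 24 stays in the late-toxicity denominator (16.1.1) after his scheduled assessments have stopped. That effect is small and does not materially change the stated error rates.

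**Working it through.** **Is survival follow-up required anywhere else?**

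- Section 4.0 lists tests, toxicity assessments and questionnaires. It has no vital-status row.
- Section 18.1 has a form called "Post Radiation Patient Status/Assessment", scheduled in active and event monitoring. Nothing says that it continues after a 13.6 exit.
- Section 10.4.1 covers deaths within 30 days of the last study treatment or procedure, and later deaths only if at least possibly related to radiation. An ordinary prostate-cancer death after recurrence falls outside it.
- Section 18.2.1 mentions vital status only for patients who revoke authorization.
- Section 11.2.6.1 needs an investigator's attribution, but nothing says how a death after exit becomes known.

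**The plan's own figures.** No power or precision is stated for 5-year survival. The only design figures are in 16.2.4. The exact probabilities of at most 4 events in 51 are 0.016, 0.102, 0.413 and 0.890, matching the stated 0.02, 0.10, 0.41 and 0.89. This point does not depend on them.

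**Inputs for the size of the bias.**

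- From Section 1.6: the photon study of the same fractionation reports 5-year survival of 92.2% and PSA relapse-free rate of 83.7%, so PSA relapse is 100 - 83.7 = 16.3%. This serves as an upper bound for clinical recurrence.
- From 16.2.2: at most 56 patients.
- Assumed, not in the documents: 5-year clinical recurrence p = 5%, 10% or 16.3%; prostate-cancer death hazard after recurrence m = 0.1, 0.2 or 0.4 per year; constant hazards; no death after recurrence becomes known.

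**Formulas.** Let recurrences begin at a lag of 0 or 2 years, with L = 5 - lag and r = -ln(1 - p)/L.

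- True disease-specific survival: S = exp(-rL) + [r/(m - r)] x [exp(-rL) - exp(-mL)].
- If censored at recurrence, disease-specific survival reads 100% and overall survival reads 0.922/S.
- Prostate-cancer share of the mortality hazard: ln S / ln 0.922.

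**Example (p = 10%, m = 0.2, no lag).** r = -ln(0.9)/5 = 0.02107 and r/(m - r) = 0.1178. S = 0.9 + 0.1178 x (0.9 - 0.3679) = 0.9627. Overall survival reported = 0.922/0.9627 = 0.958.

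The six settings in which prostate cancer accounts for no more than half of deaths, with no lag:

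| p / m | True disease-specific survival (reported about 100%) | Overall survival reported (true 92.2%) | Prostate-cancer deaths missed, of 56 | Prostate-cancer share |
|---|---|---|---|---|
| 5% / 0.1 | 98.9% | 93.2% | 0.6 | 13% |
| 5% / 0.2 | 98.1% | 93.9% | 1.0 | 23% |
| 5% / 0.4 | 97.1% | 94.9% | 1.6 | 36% |
| 10% / 0.1 | 97.8% | 94.2% | 1.2 | 27% |
| 10% / 0.2 | 96.3% | 95.8% | 2.0 | 47% |
| 16.3% / 0.1 | 96.4% | 95.6% | 1.9 | 45% |

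The bias is 1.1-3.7 points for disease-specific survival and 1.0-3.6 points for overall survival. Implied other-cause 5-year mortality is 4.2-6.8%. Missed deaths allow for other causes as a competing risk.

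**Settings set aside.** 10%/0.4 and 16.3%/0.2 give biases of 5.6-6.1 points, but they imply other-cause mortality of about 2% against a cited median age of 71. 16.3%/0.4 gives S = 90.6%, below 92.2%, so it is infeasible.

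**Sensitivity.**

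- *Delayed recurrence.* With a 2-year lag, suggested by the 28 months of androgen deprivation in Section 7.0, the same six settings give biases of 0.7-2.5 points (disease-specific) and 0.6-2.4 points (overall), with 0.4-1.4 deaths missed.
- *Partial ascertainment.* At 10%/0.2, if 0, half or all later deaths are counted while recurred survivors stay censored at recurrence, disease-specific survival reads 100.0%, 98.0% and 96.1% (true 96.3%). Overall survival reads 95.8%, 93.8% and 91.9% (true 92.2%).
- *Simulation.* Kaplan-Meier simulation of the six settings at both lags agrees within about 0.1-0.2 points.
- *Scale.* Two deaths in 56 give 96.4% survival with an exact 95% interval of 87.7-99.6%.

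**The case against.** The strongest reply is that 13.6 ends tests, not data. Where Section 13 means data to stop, it says so (13.1, 13.3). The status form in 18.1 runs to 60 months, its phases are defined only by time since radiotherapy, and a footnote waives the examination in event monitoring. Such a form could continue without any scheduled test. A disease-specific survival endpoint also makes little sense unless deaths after recurrence are collected, so a reading that preserves it deserves some weight.

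This shows that the text is ambiguous, not that follow-up is secured. Going off study most naturally ends participation. Sections 13.2 and 13.4 show that the plan states continued monitoring where it wants it. The fields of the 18.1 form are not in the documents, so whether it records vital status is unknown. Even on the favourable reading, 13.6, 18.1 and 16.3.2 need reconciling.

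Other parts of the reply stand. The size rests on assumed rates and is within sampling error. Both endpoints are descriptive. The upward direction holds when most later deaths go unseen. If every later death is counted but recurred survivors are censored at recurrence, the estimates fall slightly below the truth, by at most about 0.6 points. That also calls for a censoring rule.

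**Conclusion.** The concern holds, conditionally: if data collection ends at the 13.6 exit, 5-year disease-specific and overall survival are biased upward. In the plausible settings the bias is about 1 to 4 points for each endpoint, with disease-specific survival reported as about 100% when the truth is 96.3-98.9%. It roughly halves if half of the later deaths become known and nearly vanishes if all do.

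The size depends on assumed recurrence rates and death hazards. The direction depends on higher mortality after recurrence and on most later deaths going unrecorded. Disease-free survival is unaffected, because recurrence is already its event, and the 51-patient decision rule is not materially affected. This should be fixed because the error is systematic and the remedy is cheap. It does not threaten the primary conclusion.

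**What to change.** - **13.6:** state that a patient with local, regional or distant recurrence stops protocol-scheduled disease tests but remains in event monitoring for vital status and cause of death to 5 years from registration. Preferably, also continue recording late GI and GU toxicity to post-RT month 24. This last part matters less and can be dropped without losing the main gain.
- **13.5:** state that patients with PSA-only relapse remain in event monitoring once further management begins.
- **4.0 and 18.1:** show this follow-up in the schedule and on the forms.
- **16.3.2.2 and 16.3.2.3:** state that survival is censored at last known vital status, not at recurrence, and that deaths from other causes are censored for disease-specific survival.

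The cost is one amendment plus chart or phone checks on about 3-9 of 56 patients. 56 x p gives 2.8, 5.6 and 9.1 at recurrence of 5%, 10% and 16.3%, or 2.7, 5.4 and 8.9 once earlier deaths are allowed for. The vital-status part fits within the existing 5-year limit and adds no procedure. The optional toxicity part needs grading and attribution to proton therapy, for which 10.2.2 already provides the categories. If the sponsor already intends this follow-up, the amendment only writes it down.

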14.0 Body Fluid Biospecimens

Not applicable

15.0 Drug Information

Not applicable

16.2.2 Sample Size: This study is expected to require a maximum of 51 evaluable patients. We anticipate accruing 5 additional patients to account for ineligibility, cancellation, major treatment violation, or other reasons. Therefore, this study is expected to accrue a maximum of 56 patients overall.

16.2.3 Accrual Rate and Study Duration: The anticipated accrual rate is approximately 3-4 patients per month. Therefore, the accrual period for this phase II study is expected to be approximately 1.5 years. The final analysis can begin as soon as the last patient has been observed for 2 years, or at approximately 3.5 years after the study opens to accrual.

16.2.4 Assuming that the number of late grade 3 or higher GI or GU toxicities is binomially distributed, with a significance level of 10%, the probability of declaring that the regimen warrants further studies (i.e., statistical power) under various toxicity proportions can be tabulated as a function of the true toxicity proportion as shown in the table below.

If the true late toxicity rate is...	0.20	0.15	0.10	0.05
--------------------------------------	------	------	------	------

Then the probability of declaring that the regimen is promising and warrants further study is...	0.02	0.10	0.41	0.89
--	------	------	------	------

16.2.5 Other considerations: Adverse events, quality/duration of response, and patterns of treatment failure observed in this study, as well as scientific discoveries or changes in standard care will be taken into account in any decision to terminate the study

16.3 Analysis Plan

16.3.1 Primary Outcome Analyses:

16.3.1.1 Definition: The primary endpoint of this trial is the proportion of patients who experience a late grade 3 or higher GI or GU toxicity. Toxicity will be defined as an adverse event possibly, probably, or definitely related to proton beam therapy. A late GI or GU toxicity will be defined as a GI or GU toxicity that occurs between 3 months and 2 years from the completion of proton beam therapy. All patients meeting the eligibility criteria who have signed a consent form and have begun treatment will be evaluable for late toxicity, with the exception of patients determined to be a major violation.

16.3.1.2 Estimation: The proportion of grade 3 or higher GI or GU toxicities will be estimated by the number of patients with a late grade 3 or higher GI or GU toxicity divided by the total number of evaluable patients. Exact binomial 95% confidence intervals for the toxicity proportion will be calculated.

16.3.2 Secondary Outcome Analyses:

16.3.2.1 Disease-free survival is defined as the time from registration until the time of the first occurrence of biochemical failure (Section 11.2.1), local recurrence, regional recurrence, distant metastases, or death due to any cause. The distribution of disease-free survival will be estimated using the method of Kaplan-Meier. The disease-free survival rate will be estimated at 2 years and 5 years.

16.3.2.2 Disease-specific survival is defined as the time from registration until the date of death due to prostate cancer (Section 11.2.6). The distribution of disease-specific survival will be estimated using the method of Kaplan-Meier. The disease-specific survival rate will be estimated at 2 years and 5 years.

16.3.2.3 Overall survival is defined as the time from registration until the death due to any cause (Section 11.2.7). The distribution of overall survival will be estimated using the method of Kaplan-Meier. The overall survival rate will be estimated at 2 years and 5 years.

16.3.2.4 An acute adverse event is defined as an adverse event that occurs any time between registration and 3 months after the completion of proton beam therapy. The rate of \geq grade 3 GI or GU acute adverse events will be estimated by the number of patients with a \geq grade 3 GI or GU acute adverse event divided by the total number of evaluable patients. Exact binomial 95% confidence intervals for the true rate of \geq grade 3 GI or GU acute adverse events will be calculated.

16.3.2.5 A late adverse event is defined as an adverse event that occurs any time between 3 months and 2 years after completion of proton beam therapy. The rate of \geq grade 2 GI or GU late adverse events will be estimated by the number of patients with a \geq grade 2 GI or GU late adverse event divided by the total number of evaluable patients. Exact binomial 95% confidence intervals for the true rate of \geq grade 2 GI or GU late adverse events will be calculated.

16.3.2.6 Adverse Events: All eligible patients that have initiated treatment will be considered evaluable for assessing adverse event rate(s). The maximum grade for each type of adverse event will be recorded for each patient, and frequency tables will be reviewed to determine patterns. Additionally, the relationship of the adverse event(s) to the study treatment will be taken into consideration. Acute and late adverse events (as defined in sections 16.3.2.2 and 16.3.2.3) will be summarized separately.

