7.2 Concurrent androgen deprivation therapy

As part of the standard of care, adjuvant androgen deprivation therapy is added to proton beam therapy for 2-3 years for high risk prostate cancer, and 4-6 months for intermediate risk prostate cancer. Androgen deprivation therapy usually starts 2 months prior to the beginning of proton beam therapy. It consists of bicalutamide 50 mg PO once daily for 2-16 weeks (given at the start of androgen deprivation therapy) and a LHRH agonist (goserelin or leuprolide). The first injection of a LHRH agonist is usually given within 7 days after the initiation of bicalutamide.

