11.0 Treatment Evaluation

- 11.1 No evidence of disease: No clinical evidence of tumor recurrence including the freedom from biochemical (PSA) failure (Section 11.2.2.1)
- 11.2. Recurrence of disease: The site of recurrence will be collected, and classified as biochemical failure, local recurrence, regional recurrence and/or distant recurrence.
 - 11.2.1 Biochemical (PSA) failure: PSA nadir is defined as the lowest PSA value reached after completion of treatment. Biochemical failure is defined as a PSA value that is \geq PSA nadir + 2.0 ng/mL with the date of biochemical failure set at the date of the PSA value that meets this criterion.
 - 11.2.2 Local recurrence: Local recurrence is defined when one or more of the followings occur: (1) ureteric obstruction at the level of the ureterovesical junction; urethral obstruction that requires prostatic resection (with resected tissue demonstrating prostatic adenocarcinoma) or urinary diversion; or hematuria due to prostate cancer progression, (2) positive prostate biopsy at \geq 24 months from the completion of protocol treatment (3) \geq 20% increase in the longest diameter of a target lesion in the prostate gland (for patients with a measurable target lesion at baseline), or a new lesion measuring \geq 1 cm short axis during follow-up (for patients with non-measurable lesion at baseline) in the setting of biochemical failure

11.2.3 Regional recurrence: Development of nodal metastasis in the pelvis which is defined as a new regional pelvic node that was normal at baseline (< 1.0 cm short axis) and increased to \geq 1.0 cm short axis during follow-up. Confirmation by biopsy is encouraged.

11.2.4 Distant recurrence: Development of nodal metastasis outside the pelvis, or a hematogenous (e.g., osseous, hepatic, etc.) lesion. Confirmation by biopsy is encouraged.

11.2.5 Disease-free survival: Disease-free survival duration will be measured from the date of registration to the date of biochemical, local, regional, or distant recurrence or the date of death from any cause.

11.2.6 Disease-specific survival: Disease-specific survival duration will be measured from the date of registration to the date of death due to prostate cancer. Death due to prostate cancer will be defined as:

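### Disease-free survival has no rule for salvage therapy started before PSA reaches nadir + 2, so such failures can be counted late or not at all

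*Combined protocol and SAP*

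**What the plan says.** Two sections define DFS, and they agree. Section 16.3.2.1 counts the "first occurrence of biochemical failure (Section 11.2.1), local recurrence, regional recurrence, distant metastases, or death due to any cause". Section 11.2.5 runs from the "date of registration to the date of biochemical, local, regional, or distant recurrence or the date of death from any cause". Neither list contains a treatment-based event.

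Section 11.2.1 sets the PSA component as a value at or above "PSA nadir + 2.0 ng/mL with the date of biochemical failure set at the date of the PSA value that meets this criterion". On the reference value it says "PSA nadir is defined as the lowest PSA value reached after completion of treatment". It has no rule for PSA values taken after new hormone therapy has begun.

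Section 13.5 covers a man with biochemical recurrence only: "he will continue on the protocol test schedule until further medical management is implemented at the discretion of his physician". By then his event has been counted. No section prohibits salvage therapy below the threshold, counts it as an event, or censors at it.

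The data collection is partly in place. Section 18.1 has an androgen deprivation form, and its footnote 4 says "Coordinator will look to see if patient received Androgen Deprivation Therapy since the previous reporting period". The DFS definition does not use that form.

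**The concern.** The PSA component is judged on a marker that salvage hormone therapy is given to lower. The protocol itself treats androgen deprivation (ADT) as something that alters PSA: Section 12.3 takes the baseline PSA from just before neoadjuvant ADT. The follow-up endpoint has no matching safeguard.

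If a physician acts on a rising PSA before it reaches nadir + 2, the man counts as disease-free when salvage starts, and the treatment may then keep him below the threshold. Such an omission can only remove or delay events, so the error runs one way. Its size would depend on how early physicians intervene, which is not a property of the regimen.

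At stake is objective 2.2.3. Section 1.8 says the study may show therapeutic efficacy and could be a basis for a phase III trial.

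**Working it through.** **Inputs.**
- N = 56 accrued, 51 evaluable (Section 16.2.2).
- 5-year failure rate, assumed: 100 - 83.7 = 16.3%, from the photon series with the same dose schedule, up to 21.4% and 23.3%, the two arms of the phase III trial of 76 Gy against 70.2 Gy (both in Section 1.6).
- k, the number of men whose event is lost by 5 years: not given anywhere in the documents.

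**1. The plan's own figure.** No design figure is stated for DFS. The only one is the table in Section 16.2.4, the probability of 4 or fewer toxicities in 51 men. Exact binomial values at true rates 0.20, 0.15, 0.10 and 0.05 are 0.016, 0.102, 0.413 and 0.890, against the printed 0.02, 0.10, 0.41 and 0.89. The table reproduces. It depends on late toxicity only, so nothing below changes it.

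**2. One hypothetical man through the rules.** His nadir is 0.1, so his threshold is 2.1. PSA rises to 1.6, ADT is restarted, and PSA falls to 0.05. The restart is not an event. Because the nadir has no cut-off date, it becomes 0.05 and the threshold 2.05. He has an event only if PSA later reaches 2.05, or on clinical recurrence or death.

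The clinical components are a weak backstop while PSA is suppressed:
- Section 4.0, footnote 4, has post-RT CT/MRI and bone scan only at relapse.
- The imaging criterion for local recurrence in Section 11.2.2 is tied to biochemical failure.
- A positive biopsy counts from 24 months, but Section 4.0 schedules no follow-up biopsy.

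**3. Size per man.** With complete follow-up the Kaplan-Meier estimate at 5 years is 1 - E/N, where E is the number of events. If k events are lost it becomes 1 - (E - k)/N, a rise of k/N:
- N = 56: 1/56 = 1.8 points per man.
- N = 51: 1/51 = 2.0 points per man.

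**4. What that does to the estimate (N = 56).** The values of k show scale only.

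| Assumed failures E | k = 0 | k = 1 | k = 3 | k = 5 |
|---|---|---|---|---|
| 9 (56 × 0.163 = 9.1) | 83.9% | 85.7% | 89.3% | 92.9% |
| 12 (56 × 0.214 = 12.0) | 78.6% | 80.4% | 83.9% | 87.5% |
| 13 (56 × 0.233 = 13.0) | 76.8% | 78.6% | 82.1% | 85.7% |

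**5. Would censoring do instead?** Take N = 56 with 12 failures spread evenly from 2.5 to 4.9 years, 3 of them salvaged early, and everyone else followed past 5 years. The 5-year DFS is 78.6% if the 3 count as events, 83.9% if they are ignored, and 83.5% if they are censored. Censoring removes almost none of the bias.

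**The case against.** The strongest reply is that little rests on this endpoint. DFS is secondary, in a single arm, with no threshold or test. At a 16.3% failure rate and N = 56, the approximate 95% half-width is 1.96 × √(0.163 × 0.837/56) = 9.7 points, against 1.8 points per missed man. That stands, and it makes this an improvement rather than a necessity. It does not remove the bias, because a wide interval does not correct a one-sided error.

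The remedy also has a cost. Counting a treatment decision changes the endpoint from recurrence or death to something that partly reflects physician intent. The cited series, as summarised, mention no salvage component, so a changed definition may be less comparable with them. This also stands, and it is why the current definition should be reported alongside.

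A reader might go further on four points that the documents do not support:
- *That a rescued man is scored disease-free for good.* He remains at risk of a later PSA rise to the threshold, clinical recurrence or death. Some events are delayed, not lost.
- *That the overstatement can be put at several points.* That needs a value of k, and no section suggests one.
- *That each man removes 11% of expected DFS events.* 1/9.1 = 11% is a share of PSA relapses. Adding deaths from the same series (100 - 92.2 = 7.8%; 56 × 0.078 = 4.4), if none overlap, gives 13.5 events and a share of about 7%.
- *That ADT can be lengthened in response to PSA without leaving the protocol.* Section 7.2 says "adjuvant androgen deprivation therapy is added to proton beam therapy for 2-3 years for high risk prostate cancer", but Section 7.0 states 28 months. Until these are reconciled, the documents do not settle what counts as an extension.

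**Conclusion.** The gap is real and worth a cheap correction. As written, salvage therapy started for a rising PSA before nadir + 2 is neither an event nor otherwise handled, so 5-year DFS and freedom from PSA relapse can be biased upward. The size is about 1.8 points (N = 56) or 2.0 points (N = 51) for each man whose event is lost by 5 years, ignoring censoring. The total cannot be stated, because the frequency of such salvage is unknown and some events would only be delayed. The failure rates used for illustration come from cited photon studies and are assumptions for this trial; the documents do not say how those studies handled early salvage. A reader might infer that the trial's decision is at risk. It is not: the rule of 5 or more toxicities in 51 men, the sample size and the power do not involve DFS.

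**What to change.** In Sections 11.2.5 and 16.3.2.1, add as a DFS event, dated at its start: *the start of salvage anticancer therapy for prostate cancer, meaning new or restarted ADT after the planned course, radiotherapy, surgery or other systemic therapy, given for rising PSA or suspected recurrence*. Report DFS under the current definition alongside it as a sensitivity analysis.

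Three supporting changes are needed:
- Record each man's planned ADT course at registration.
- Add a reason field to the existing ADT form and a salvage-treatment item to the post-radiation status form. Section 18.1 names no form for salvage radiotherapy, surgery or other systemic therapy.
- Reconcile the ADT durations for high-risk men in Sections 7.0 and 7.2, so that planned ADT is not counted as an event. Which duration applies is for the investigators to state.

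The cost is an amendment to protocol text as well as analysis text, plus a few data fields. No patient numbers, visits or tests change. The downsides are that DFS may be slightly lower, that a man treated without true recurrence becomes an event, and that comparability with the cited series is kept only through the current-definition analysis.
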